Interested parties will be provided with a telephone number and electronic mailing address to contact study personnel for more information regarding the study. A verbal consent form followed by a brief telephone screen will be used to assess initial eligibility; if research participants meet inclusion criteria based on the screening, the research participant will be scheduled for an initial clinical assessment with a trained assessor. If the research participant reports use of compensatory behaviors 3 or more times per week (i.e., purging and/or using laxatives), or endorses medical symptoms related to their eating disorder on the phone screen, we will ask the research participant to receive medical clearance from his or her PCP prior to enrollment in the study to ensure the research participant is safe to receive outpatient treatment. If the research participant refuses to obtain medical clearance or receive medical monitoring as requested by the study, they will be informed that they will not be eligible for participation in the study. Materials for their PCP will be mailed or emailed to research participants so they can obtain medical clearance for participation prior to their initial clinical assessment visit. Written or electronic informed consent will be obtained at the clinical assessment. The consent form will contain all pertinent details of the study procedure. Research participants will be clearly informed of the voluntary and confidential nature of their participation, and their right to terminate treatment at any time without penalty. After

PROTOCOL TITLE: Using factorial design to examine efficacies of technology-based augmentations for improving treatment adherence and skills utilization in a self-help CBT program for binge eating.

Protocol Version Date: April 19, 2022

research participants read the consent form, the program staff will paraphrase each segment of the consent form and will answer any questions. If the research participant agrees to participate, the consent form will be signed and witnessed. If the research participant chooses not to participate, they are given the option to be added to our study database to be contacted for other studies they might be eligible for at the WELL Center in the future. They will also be offered referral lists for other resources if they are interested. If they choose not to be entered into the database, all their information will be destroyed upon the completion of the study.

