Patients with frequent or and intense eating disorder pathology, or medical symptoms related to their eating disorder must receive clearance from their primary care physician (PCP) before they can be considered eligible for participation in this study. PCPs will be asked to provide measurements of height, weight, vital signs, and blood draws. PCPs will be notified via letter of their role in determining eligibility for the study and will be provided contact information for the study PI if they have any questions or concerns. Individuals who are or become medically unstable for outpatient treatment will be referred for appropriate medical treatment. Patients must also agree to allow study staff to communicate with their PCP throughout the study and to be reassessed for medical stability if there is a worsening in symptoms. Once a participant is enrolled in the study, study therapists/staff and the PCP will jointly determine the appropriate level of medical care outside of study visits to ensure the participant remains medically stable for outpatient treatment. If patients become medically unstable for outpatient treatment or show a significant and continued worsening in symptoms, they will be removed from the study and referred to a higher level of care. The procedures for medical management of the study patients described above have been successfully utilized by our lab in prior studies of patients with binge eating spectrum disorders. After potential participants are deemed eligible a baseline assessment will be completed. If participants are found to be ineligible at any stage of the process, participants will be given referrals if desired.

Following the baseline assessment, participants will be randomized to receive one of the four treatment conditions and will receive 12 weeks of treatment.

Plans for assessing and/or intervening on suicidal ideation or risk for serious self-harm.

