Eating disorders are associated with suicidality and studies utilizing eating disorder samples have a plan to ensure the adequate assessment and treatment of suicidality. If study staff or clinicians become aware of a clinically significant increase in depression or the emergence of suicidal ideation or self-harm behavior, the participant will undergo a comprehensive assessment of suicide ideation, plan, and intent with [name] (a Licensed Clinical Psychologist), and the necessary precautions will be taken to ensure safety or medical attention as appropriate. If high acute risk for suicidal ideation is discovered, [name] will make a telephone connection to a crisis resource (i.e., 24-hour crisis lines at [contact]) while maintaining contact with the participant in order to make a direct transfer. In addition, [name] will also immediately connect these participants with mental health emergency for hospitalization. These participants will be removed from the study so their suicidal ideations can be fully addressed. If intermediate acute risk and low acute risk for suicidal ideation is discovered, [name] will provide participants with contact information for mental health care provider and will be instructed to use mental health resources in case of psychiatric emergency or suicidality (i.e., 24-hour crisis lines at [contact]) that occurs outside of standard business hours when [name] could not be reached. These participants will be allowed to continue their study participation. [name] will maintain contact

PROTOCOL TITLE: Using factorial design to examine efficacies of technology-based augmentations for improving treatment adherence and skills utilization in a self-help CBT program for binge eating.

Protocol Version Date: April 19, 2022

mental health provider to determine acuity of referral. This method for assessing and intervening on suicidal ideation or risk for serious self-harm is currently standard practice in the WELL clinic and has been used successfully in our other clinical trials for BN and BED.

Ensuring participants receive high-quality interventions.

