Research participants will be withdrawn from the study if they no longer meet the study criteria and/or they experience any acute life-threatening incident (precipitous drop in weight, change in electrolyte balance, etc.), hospitalization, suicidal or homicidal ideation, or serious self-harm behavior, failure to comply with study procedures. Condition of pregnancy will be assessed during the baseline, mid-treatment, post-treatment, and 3 month follow-up. If the research participant finds out that they are pregnant or plan on becoming pregnant within the next year during their time in the study, they must notify the project coordinator immediately. They will no longer meet study criteria and will be withdrawn from the study immediately. If termination is found necessary, the research participant will be contacted by the project coordinator immediately and the necessary precautions will be taken to ensure safety or medical attention as appropriate. The research participant will then be provided with referrals to other programs or studies if applicable and the data will be destroyed/banned from use. If, at any time, the treating physician determines that the health of the research participant precludes continuation of outpatient treatment, a meeting will be scheduled with the treating physician, research participant, and study staff to assist in locating referrals for appropriate levels of care. If a higher level of care is sought, research participants will be removed from the trial. Research participants are given the option to be added to our study database to be contacted for other studies they

PROTOCOL TITLE: Using factorial design to examine efficacies of technology-based augmentations for improving treatment adherence and skills utilization in a self-help CBT program for binge eating.

Protocol Version Date: April 19, 2022

might be eligible for at the WELL Center in the future. If they choose not to be entered into the database, all their information will be destroyed.

15) Risk to Subjects

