Some research participants undergoing treatment may become uncomfortable or anxious. Research participants will be asked to abstain from binge eating and purging, a process that is difficult given the nature of the illness. Research participants will also be asked to provide information regarding a number of significant health behaviors during the assessments. However, all assessment instruments have been used in past research without incidence and research participants will be informed that they can skip questions or discontinue participation at any time. Although we expect most research participants to show a reduction in disordered eating symptoms, it is possible that some research participants could experience a worsening of eating disorder symptoms during the study period. If a worsening of symptoms is identified, we will follow the protocol described below to ensure the safety of research participants. This protocol is based on those used in our team's current NIH funded trials for BN and BED. If a coach identifies worsening binge eating symptoms or compensatory behaviors, the principal investigator and research coordinator will be notified. If the increases in disordered eating symptoms are determined to be transient, mild, and unlikely to result in adverse health consequences, efforts will be made to keep the research participant enrolled in the current study and treatment condition consistent suggestions will be made to address current symptoms. If the increases in eating disorder symptoms are sustained, clinically significant, or likely to cause health consequences, we will consult with the research participant's PCP to discuss whether medical management is needed. Research participants with frequent and intense eating disorder pathology will be medically monitored by their PCP throughout the trial and will only be allowed to participate if it is deemed medically appropriate by their PCP. Research participants will be informed that research personnel will inform the PCP if there is a change in symptom status such as an increase in restrictive eating behavior or increase in purging behavior that may require additional medical management. It is expected that these research participants will have regular appointments with their PCP, the frequency of which will be determined by the treating physician. In order to facilitate care, consent will be obtained prior to treatment onset for two-way communication between study staff and the treating physician. As part of the trial, treating physicians will also be provided current practice guidelines as set forth by the American Academy of Psychiatry regarding eating disorders. Research participants without a PCP, with limited access to their PCP, or with a PCP that is unable to effectively monitor their eating disorder symptoms, will be assisted in locating a PCP that better fits their needs. We will not be

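### Protocol section 14 destroys or bans the data of participants whom the study terminates, so randomised people can leave the analysis and the SAP's missing-data methods lose their partial records; the effect is probably small and the fix is cheap

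*Protocol*

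**What the plan says.** Protocol section 14 (Withdrawal of Subjects) lists the grounds on which the study withdraws a participant: no longer meeting study criteria, an acute life-threatening incident, hospitalisation, and "suicidal or homicidal ideation, or serious self-harm behavior, failure to comply with study procedures". Pregnancy, or a plan to become pregnant within the year, is added. If termination is found necessary, the participant is contacted, made safe, and then "provided with referrals to other programs or studies if applicable and the data will be destroyed/banned from use". The section closes with a second rule, tied to the contact database for future studies: "If they choose not to be entered into the database, all their information will be destroyed".

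Other sections bear on how far this reaches:

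- Section 10, Screening: "If patients become medically unstable for outpatient treatment or show a significant and continued worsening in symptoms, they will be removed from the study". Section 10 (Blood Draws) and section 15 also remove people for unsafe purging or for needing a higher level of care. None of these mentions data destruction.
- Section 10, suicidality plan, for low and intermediate acute risk: "These participants will be allowed to continue their study participation".
- Section 15, for mild or transient worsening: "efforts will be made to keep the research participant enrolled in the current study".
- Section 24 encourages people who stop treatment to stay in the assessments. It does not cover people whom the study removes.

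The SAP (Statistical Design and Power) plans likelihood-based estimation and multiple imputation, with sensitivity analyses if missingness depends on the outcome itself. Its Aim 2 sets a retention target above 75%.

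**The concern.** Every section 14 trigger can occur after randomisation, and some can relate to the outcomes: safety events to clinical state, and non-compliance (undefined) to the adherence target of Aim 1. If the rule is followed, two things happen. The ON versus OFF comparison is no longer fully as randomised. And the baseline and mid-treatment records that likelihood and imputation methods use to correct for dropout are missing for just these people. Destroyed data cannot be recovered by any later analysis.

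Unequal loss is conceivable for the data-sharing factor. Section 15 says "If a coach identifies worsening binge eating symptoms or compensatory behaviors, the principal investigator and research coordinator will be notified", whereas with that factor OFF the participants' data are not shared with coaches. Removing more of the worst cases from ON would flatter ON. No such route is apparent for the JITAI factor.

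**Working it through.** **1. The plan's own sample size, to see whether power is at stake.** From the SAP Power Analysis: d = 0.78, four assessments, variance ratio 1, alpha 0.05, N = 64, 15% attrition. With straight-line change, λ = N·d²·τ / [4(τ + V)] and V = σ²/Σ(t − t̄)². Four unit-spaced times give Σ = 5, so V = 0.2 and λ = 64 × 0.6084 / 4.8 = 8.11; the noncentral F(1, 62) gives 80.1%. Then 64/(1 − 0.15) = 75.3, rounded up to 76. Both stated figures reproduce. Six deletions leave 70, above 64 (power 83.6%, against 86.5% at 76).

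The Aim 1 calculation has no attrition allowance. For a test with exactly 80% power at 76, power ≈ Φ(2.80·√(N/76) − 1.96), which is 79%, 78% and 77% at N = 74, 72 and 70. Power is therefore not the argument.

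**2. Bias and false positives.** The documents give no number terminated, so these inputs are assumptions: 38 per factor level (76/2), a normal outcome, no true effect, a withdrawal trigger correlated ρ with the outcome, and removal when the trigger passes a fixed cut-off c chosen so that a fraction q = k/38 is removed. The remaining mean shifts by −ρ·φ(c)/(1 − q).

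For ρ = 0.5:
- ON, k = 4: q = 0.105, c = 1.252, φ = 0.182, shift −0.102.
- OFF, k = 2: q = 0.053, c = 1.620, φ = 0.107, shift −0.057.
- Difference: 0.045 SD in favour of ON.

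If instead one cut-off (k = 4) applies to both levels and half of the OFF cases go undetected, the OFF shift is −0.5 × 0.5 × 0.182/0.947 = −0.048, and the difference is 0.054.

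False positives come from simulation (200,000 runs per case, pooled two-sided t-test):

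| Expected removals ON/OFF | Bias, ρ = 0.5 (0.3) | False positives, ρ = 0.5 (0.3) |
|---|---|---|
| 0/0 | 0.00 (0.00) | 5.0% (5.0%) |
| 3/3 | 0.00 (0.00) | about 5.0% (5.0%) |
| 4/2 | 0.04–0.05 (0.03) | 5.4–5.7% (about 5.1%) |
| 4/0 | 0.10 (0.06) | 7.2% (5.8%) |
| 6/0 | 0.14 (0.09) | 9.1% (6.5%) |

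This is the simple post-treatment contrast listed under SAP Aim 3. The SAP's main test, the time-by-factor interaction, was not modelled, and no bias figure is offered for Aim 1.

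**3. What keeping the data would recover.** Assume 4 ON/2 OFF removed, correlation 0.5 between visits, and ρ = 0.5. Deletion bias is 0.04 to 0.05 SD. A likelihood analysis of the retained records leaves 0.00 if termination follows a recorded mid-treatment score, 0.01 if half leave before that visit and 0.02 if all do. It leaves 0.02 to 0.04 if half of the link runs through things not recorded, and gains nothing if all of it does.

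**4. Aim 2 retention.** If terminated people also leave the denominator, c completers turn a fail into a pass when c/76 ≤ 0.75 and c/(76 − k) > 0.75. Since 0.75 × 76 = 57, this happens for c = 56–57 (k = 2), 55–57 (k = 4) and 53–57 (k = 6). For example, 54/76 = 71.1% but 54/70 = 77.1%.

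**The case against.** Much can be said against making this large, and most of it stands.

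- **Reach.** A reader might infer that everyone removed for worsening has their data destroyed. The sections that remove people for worsening or instability speak only of removal and referral, and in section 14 itself the higher-level-of-care removal comes after the destruction sentence without repeating it. The extension is possible but inferred. The destruction sentence also directly follows the pregnancy text, although its reference to safety and medical attention fits all triggers better. Reading non-compliance as low app use is likewise unsupported.
- **False positives.** One might conclude that even equal deletion inflates the error rate. It does so (to about 5.6% for 3/3 at ρ = 0.5) only if exactly the top-ranked people in each level are removed. A criterion acts as a cut-off, and then the rate stays at about 5.0%.
- **One-sided loss.** The larger figures need 4 to 6 removals in ON and none in OFF. Mid-treatment assessments, physician monitoring and pregnancy checks apply in every condition, so no document supports that.
- **Sensitivity analyses.** They are weakened, not necessarily impossible. If the allocation record survives, which section 14 does not address, scenarios by factor level can still be run. The Aim 2 effect needs that record to be erased, and nothing says it is.
- **Retention periods.** The 7-year rule covers protected health information, so it does not contradict section 14 on outcome data. Only the 3-year rule in section 12 does, and it sets a time for erasure.
- **Closing sentence.** It may be carried over from the consent procedures in section 10, where people who decline to take part are told "all their information will be destroyed upon the completion of the study".

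The consent form and one early part of the SAP were not available and could qualify the rule. What none of this removes is the sentence itself: no text available exempts data already collected.

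**Conclusion.** The point holds as a harmful stated rule of modest effect. Section 14, taken at its word, takes the data of study-terminated randomised participants out of use, and for those people the SAP's missing-data plan cannot be carried out as written. On the assumptions above the likely distortion is between nothing (equal loss) and 0.03 to 0.05 SD with false positives of about 5.1 to 5.7% (4 ON/2 OFF). The figures of 0.06 to 0.14 SD and about 6 to 9% belong to one-sided loss and should be read as an outer bound. All of this depends on an unstated number of terminations and an assumed correlation. The reason to act is that destruction cannot be undone and the remedy costs little. Label: cheap improvement.

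**What to change.** Replace the destruction sentence in section 14 with: *All data collected up to withdrawal are retained and analysed as randomised; data are destroyed only at the participant's explicit request.* Limit the closing sentence of section 14 in the same way. State that Aim 2 retention is counted over all randomised participants. Align the consent form. Keep the SAP's sensitivity analyses, because retained data remove the bias only so far as termination depends on what was recorded.

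Cost: an IRB wording amendment, and possibly a consent addendum for people already enrolled under the present wording. No new visits are needed, and follow-up of terminated participants is not required for this fix.

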For the study we will recruit participants from the community. Information needed to determine whether research participant meets eligibility requirements will be obtained during an initial phone-screen (see attached – using questions drawn from the Mini International Neuropsychiatric Interview (MINI)). If research participants meet the inclusion criteria based on the phone screening, they will be scheduled for an in-person or remote initial clinical assessment. Trained assessors will go through each criterion and document whether the research participant is eligible for the study using a standardized assessment checklist. If research participants meet the inclusion criteria based on the clinical assessment, they will be scheduled for an in-person or remote clinical intake. Research participants will be included if they meet the following criteria:

Individuals will be included if they:

1. Are 18 to 70 years old
2. Have experienced 12 or more loss of control episodes within the previous 3 months
3. Have a BMI above 18.5
4. Are located in the US and willing/able to participate in remote treatment
5. Are able to give consent

Individuals will be excluded from the study if they:

1. Are unable to fluently speak, write and read English
2. Are already receiving treatment for an eating disorder (e.g., research participants cannot be receiving concurrent eating disorder treatment from another provider)
3. Have a mental handicap or are currently experiencing severe psychopathology that would limit their ability to engage in study (e.g., suicidality, substance use disorder, active psychotic disorder, severe depression with suicidal intent)
4. Are purging and/or using laxatives 3 or more times per week and are not deemed safe for outpatient treatment by a primary care provider
5. Are unwilling to receive medical clearance and/or medical monitoring as requested by the study to ensure they are medically safe to participate
6. Are pregnant or planning to become pregnant within the next year
7. Are individuals who are not yet adults (infants, children, teenagers)
8. Are currently taking any of these medications: Haldol, Loxitane, Mellaril, Moban, Navane, Prolixin, Serentil, Stelaxine, Trilafon, Thoraxine, Abilify, Clozaril, Geodon, Risperdal, Seroquel, Zyprexa
9. Are adults unable to consent

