Coaches will be individuals with bachelor's degree in health-related fields (e.g., psychology, nursing, nutrition etc.) working at the WELL clinic. Coaches are research personnel and have been trained in human subject research through CITI. Coaches will receive training from [name] on reviewing participant's treatment adherence, skills utilization, and self-monitored data and to provide support to participants for improving treatment adherence and skills utilization via emails. Coaches will attend weekly group meetings with [name] to jointly review participants' treatment adherence, skills utilization, and self-monitored data and discuss ways to offer support for improving behaviors related to treatment targets via emails. All assessors will already have had prior training and experience working with individuals with eating disorders. Study personnel will receive specialized training in the administration of assessments. Training will be conducted by [name] will include, but not be limited to, review and discussion of interviews, role playing, and dry runs with practice individuals with live supervision. The project statistician will conduct randomization to prevent the assessor from being a source of bias. The content of the base self- help CBT program will be based on Chris Fairburn's evidence-based Overcoming Binge Eating book.

The standard of care for binge spectrum eating disorder and bulimia nervosa is behavioral treatment. In this project, all the participants will receive self-help CBT program based on [name] evidence based-treatment program for binge spectrum eating disorders and is superior to standard of care. As such, there is no potential of randomizing subjects into a condition that is less than standard of care for their eating disorders.

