Blood Draws. As is standard, blood testing to assess for medical complications associated with purging is conducted based on severity of purging behavior. If participants demonstrate purging 3 or more times per week and are deemed unsafe to continue study participation by their PCP, they will be removed from the study to receive medical care of worsened purging behavior, and thus, will not undergo anymore blood testing for the study assessments. If the severity of purging is low (i.e., less than 3

PROTOCOL TITLE: Using factorial design to examine efficacies of technology-based augmentations for improving treatment adherence and skills utilization in a self-help CBT program for binge eating.

Protocol Version Date: April 19, 2022

episodes per week), participants may undergo blood testing once during the study for medical monitoring and to receive PCP clearance to continue study participation in addition to study assessments.

Feasibility and Acceptability. Assessment of feasibility will include number of patients screened per month, % of eligible patients enrolled, treatment attrition (% of patients that prematurely terminate treatment), study retention (% of patients that complete all study assessments), treatment adherence, treatment fidelity. Acceptability will be assessed using the Feedback Questionnaire. During treatment each session will be audio-recorded and 20% of the sessions for each group treatment will be randomly selected for adherence and competency ratings by a blinded IE.

Outcome Measures

Rater-Administered Measures:

- ***Eating Disorder Examination (EDE)***. The EDE is a widely utilized, semi-structured interview for the assessment of eating disorder symptoms. The EDE interview will be audio recorded and will be used to confirm research participant's eligibility. The EDE has been updated to the newest version of this measure.
- ***Mini International Neuropsychiatric Interview (MINI)***. The MINI is a structured psychiatric diagnostic interview.
- ***Body Mass Index (BMI)***. For BMI, height (via stadiometer) and weight (via medical-grade, digital scale) will be assessed in the clinic prior to treatment onset and at each assessment point. This data will be used to calculate BMI. In the case of remote assessments, research participants will weigh themselves at home using digital scales and take their heights using yard sticks or measuring tape.

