Eating disorders can be medically dangerous, particularly if the individual is of low weight or engaging in frequent or severe compensatory behaviors. Thus, careful monitoring of treatment progress is essential. It is possible that some research participants may develop Anorexia Nervosa or display dangerous electrolyte imbalances due to purging. In this case, the research participant will be removed from the study and referred to a more appropriate level of care (e.g., intensive outpatient, inpatient treatment). The process for tracking this information and making referrals to a higher level of care is described below.

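### Section 14 erases the data of randomized participants whom the study withdraws, so the analyses can lose people for post-randomization reasons that may relate to outcome; the direction of any bias is unknown and its size probably small

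*Protocol*

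**What the plan says.** Protocol Section 14 (Withdrawal of Subjects) lists the grounds on which the study withdraws someone: no longer meeting criteria, an acute life-threatening event, hospitalization, suicidal or homicidal ideation, serious self-harm, non-compliance and pregnancy. Where termination is needed, the participant is referred to other "programs or studies if applicable and the data will be destroyed/banned from use". The section then adds "If a higher level of care is sought, research participants will be removed from the trial", and closes with a sentence on the contact database for future studies: "If they choose not to be entered into the database, all their information will be destroyed".

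Other sections add routes out of the trial:

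- Section 10, Screening, covers enrolled patients who become medically unstable or "show a significant and continued worsening in symptoms, they will be removed from the study and referred to a higher level of care".
- Section 10, Blood Draws, says of people purging three or more times a week whom the PCP judges unsafe that "they will be removed from the study to receive medical care of worsened purging behavior".
- Section 15, on new anorexia nervosa or dangerous electrolyte imbalance, says "In this case, the research participant will be removed from the study".
- Section 5 requires participants to "Have a BMI above 18.5", so marked weight loss can itself end eligibility.

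These sections do not repeat the data rule, but their removals plausibly fall under it.

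Section 24 encourages people who stop treatment to keep attending assessments. It does not mention people whom the study withdraws. The SAP's opening paragraph plans likelihood-based estimation, multiple imputation and sensitivity analyses for missing data.

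**The concern.** Randomization follows the baseline assessment (Section 10), and Section 14 applies its triggers throughout participation, with pregnancy rechecked up to the 3-month follow-up. The data rule therefore reaches randomized participants. It is not leftover screening language, because Section 12 has a separate rule for screen failures.

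The planned missing-data methods work from partial records. A participant whose baseline and interim data are destroyed or barred contributes nothing to a mixed model, an imputation model or a sensitivity analysis. Such a person is removed from the comparison, not missing within it.

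That matters if removal is related to outcome and unequal across factor levels. Several triggers reflect worsening of the disorder under study, and non-compliance lies close to the Aim 1 adherence target. Two mechanisms could produce imbalance, and they pull in opposite directions:

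- With Advanced DDS ON, coaches attend weekly meetings "to jointly review participants' treatment adherence, skills utilization, and self-monitored data", and Section 15 has worsening that a coach notices reported to the principal investigator. That channel is absent with DDS OFF, so more worsening might be found, and removed, in the ON level. This would flatter DDS.
- Both factors aim to raise adherence. If they succeed, non-compliance removals would concentrate in the OFF cells. If non-compliers also do worse, erasing them flatters OFF.

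The stakes are the effect estimates. The SAP's Power Analysis says it will rely on the EDE global effect size and its interval, and offers these for designing a larger trial.

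**Working it through.** **1. The plan's own figure.** Inputs from the SAP Power Analysis: d = 0.78, four assessments, variance ratio 1, alpha 0.05 (two-sided assumed), 80% power. For a linear trend with M = 4:

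- V = 12/[(M−1)M(M+1)] = 12/60 = 0.2
- λ = N·d²/[4(1+V)] = 64 × 0.6084/4.8 = 8.11
- Noncentral F(1, 62) power = 80.06%

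So N = 64 reproduces, and 64/0.85 = 75.3, rounded up to 76. The sample size arithmetic is sound.

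**2. Precision.** The margin is 76 − 64 = 12. Losing 4 whole records and nothing else leaves 72, with power 84.6% against 86.5% at 76. Precision is not the problem; selection is.

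**3. Size of the selection effect.** The documents give no withdrawal rate, so every input here is an assumption:

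- 38 participants per factor level and no true effect
- the k = 2 to 4 worst participants per level on a trigger score meet a removal trigger
- the trigger correlates r = 0.3 to 0.6 with the analysed outcome, which is normal with SD 1
- a triggered participant is removed with probability a in one level and b in the other, with a + b = 1, so k records are lost on average

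With m the mean of the k largest of 38 standard normal values (1.93 for k = 2, 1.67 for k = 4), the approximate shift is

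r·m·[ka/(38 − ka) − kb/(38 − kb)].

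- Smallest unequal case (r = 0.3, k = 2, 60/40): 0.3 × 1.93 × (1.2/36.8 − 0.8/37.2) = 0.006 SD
- Largest case (r = 0.6, k = 4, 75/25): 0.6 × 1.67 × (3/35 − 1/37) = 0.059 SD
- Balanced (50/50): zero

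Simulation of 20,000 trials gives the same values:

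| r | split | k = 2 | k = 3 | k = 4 |
|---|---|---|---|---|
| 0.3 | 60/40 | 0.006 | 0.009 | 0.012 |
| 0.3 | 75/25 | 0.016 | 0.023 | 0.029 |
| 0.6 | 60/40 | 0.013 | 0.018 | 0.023 |
| 0.6 | 75/25 | 0.032 | 0.046 | 0.059 |

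The shift favours whichever level loses more of its worst cases. Swapping a and b reverses the sign and leaves the size unchanged.

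**4. Against sampling error.** The standard error of a difference between two groups of 38 is √(2/38) = 0.23 SD. The largest shift is 0.059/0.23, about a quarter of a standard error. That would raise a nominal 5% test to about 5.8%.

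**5. Does keeping the data help?** In a mixed model with times 0 to 3, unit variances, known covariance and removal after the second assessment, the shift in the factor-by-time slope (slope SD units) is:

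- Trigger follows observed early change (k = 4, 75/25): 0.020 at r = 0.3 and 0.040 at r = 0.6 with records destroyed; 0.000 with records kept.
- Trigger follows the unseen true slope (k = 4, 75/25, r = 1.0): 0.098 destroyed, 0.054 kept. The shift scales with r, so at r = 0.6 these are about 0.6 × 0.098 = 0.059 and 0.6 × 0.054 = 0.032.

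Keeping data removes the shift in the first case. In the second it removes 1 − 0.054/0.098 = 45%. The zero in the first case is expected, because the data are then missing at random by construction.

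**The case against.** The best reply is that few people will be affected and that the link to binge eating is loose. No Section 14 trigger names binge frequency. Section 15 tries to keep people with mild or transient worsening enrolled, and for sustained worsening it first consults the PCP; a coach's report is not itself a withdrawal trigger. Study staff download app data in every cell (Section 12), Section 13 acts whenever the team learns of worsening, and scheduled EDE interviews and PCP contact run in all four cells. Section 10 removes only people at high acute suicide risk, although Section 14 lists ideation without grading it. All of this stands, and it is why the size is put as small and the direction as unknown.

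The contact-database sentence is also weak evidence. Similar wording in the Section 10 consent procedures concerns people who decline to join, so it may have been carried over. It needs clarifying, but it should not be counted as a firm second erasure rule.

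Privacy does not answer the point, because deletion on request can be kept. Small expected numbers do not fully answer it either: once records are destroyed, nobody can check afterwards whether the loss mattered.

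**Conclusion.** The concern holds in this form: as written, the withdrawal rule takes randomized participants wholly out of the Aim 1, 3 and 4 analyses for post-randomization reasons that may relate to outcome or adherence, and the planned missing-data methods cannot recover them. The bias has unknown direction and is probably small: about 0.01 to 0.06 SD under the stated assumptions, and zero if removal is balanced. It is worth correcting because the loss is irreversible and the remedy cheap.

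Stronger readings that the documents do not support:

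- **That the rule favours DDS.** Coach detection points that way, but non-compliance removals point the other way. Loss of eligibility taken literally could even remove responders, since entry requires at least 12 loss-of-control episodes in three months.
- **That the bias is large.** That would need nearly all removals in one level, or a trigger almost identical to the outcome. Nothing in the plan suggests either.
- **That power is compromised.** Two to four lost records sit inside the margin of 12, though they would share it with ordinary attrition.
- **That the SAP lacks an all-randomized analysis set.** The supplied SAP text is incomplete, so this is not asserted. No analysis set could include destroyed records in any case.

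**What to change.** 1. Amend Section 14 so that withdrawal ends the intervention, while data collected up to that point are kept and analysed under the randomized condition unless the participant asks for deletion. Say that this also governs the removals in Sections 10 and 15, and reconcile the suicidality trigger with Section 10.
2. Clarify that declining the contact database deletes contact details only, not study data.
3. Extend the Section 24 offer of remaining assessments to participants whom the study withdraws, where safe. This addresses the part of the bias that retained data alone cannot.
4. Record the date, reason and source of detection for each withdrawal, and report counts by DDS level, JITAI level and reason.

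The cost is an IRB amendment, matching consent wording (an addendum for anyone already enrolled), three withdrawal fields and one short table. No new outcome measure is needed.
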